6.0 STUDY POPULATION

Potential subjects are men ≥ 18 years that have undergone prostate biopsy and diagnosed with adenocarcinoma of the prostate within 12 months prior to study Screening. Subjects diagnosed with either ISUP Grade Group 1 or 2 prostate cancer will undergo screening procedures to ensure that they meet the inclusion and exclusion criteria.

Subjects diagnosed with ISUP Grade Group 1 are required to have a minimum of 3 positive biopsy cores or one core with 50% or more cancer to be eligible for the study.

Subjects diagnosed with ISUP Grade Group 2 will have less than 50% of total number of any cores positive to be eligible for the study. See inclusion criteria 4 for further details.

Subjects will be stratified by 1 or >1 biopsy ≤ 12 months prior to screening that will balance between arms for the number of prior biopsies and the utilization of MRI guided biopsy for a second or confirmatory biopsy.

Approximately 450 eligible subjects will be randomized 2:1 to either sipuleucel-T arm or control arm. ISUP Grade Group 1 will be capped at 80% of study population.

Stratification will be based on:

- ISUP Grade Group 1 or 2
- Number biopsies 1 or >1 (≤ 12 months of Screening)

6.1 Inclusion Criteria

For a subject to be eligible for participation in this study, *all* of the following criteria must be satisfied.

6.1.1. Age is ≥ 18 years

6.1.2. Written informed consent provided prior to the initiation of study procedures

6.1.3. Histologically proven adenocarcinoma of the prostate initially diagnosed ≤ 12 months of Screening. All biopsy slides with subject information redacted must be submitted for BICR.

6.1.4. Prostate cancer diagnosis determined by BICR as one of the following:

- a. ISUP Grade Group 1 with 3 or more cores positive from a systemic (≥ 10 cores) biopsy.
- b. ISUP Grade Group 1 with ≥ 1 core positive with $\geq 50\%$ cancer involvement from a systematic (≥ 10 cores) biopsy

- c. ISUP Grade Group 1 from 3 or more positive cores from any combination of cores from a systematic (≥ 10 cores) biopsy and MRI targeted biopsy (note: multiple cores from each MRI targeted lesion will count as 1 core)
- d. ISUP Grade Group 1 from a negative systematic (≥ 10 cores) biopsy and an MRI targeted core positive with $\geq 50\%$ cancer involvement
- e. ISUP Grade Group 2 from a systematic (≥ 10 cores) biopsy (with $< 50\%$ of the total number of any cores positive for cancer)
- f. ISUP Grade Group 2 from a negative systematic (≥ 10 cores) biopsy and MRI targeted core(s) positive for Gleason 3+4 (see note below)
- g. ISUP Grade Group 2 from any combination of cores from a systematic (≥ 10 cores) biopsy and MRI targeted biopsy (see note below)

Note for f and g: the total number of positive cores must be $< 50\%$ of total cores from both the systematic biopsy and MRI targeted lesions; each MRI targeted lesion, irrespective of multiple positive cores, will each count as 1 core for the total number of positive cores, e.g., 4 targeted lesions with 2 positive cores each will only add 4 to the total core count). Subject consents to standard of care for biopsy frequency of 2 on-study prostate biopsies and to provide biopsy tissue for study endpoint analysis.

- 6.1.5. Estimated life expectancy ≥ 10 years
- 6.1.6. Candidate for primary curative therapy (e.g., surgery or radiation) if prostate cancer progression occurs
- 6.1.7. Eastern Cooperative Oncology Group (ECOG) performance status of 0 or 1
- 6.1.8. Adequate baseline hematologic, renal, and liver function tests as evidenced by laboratory test results within the following ranges ≤ 30 days prior to randomization
 - White blood cell (WBC) count $\geq 3.0 \times 10^6$ cells/mL
 - Absolute neutrophil count (ANC) $\geq 1.5 \times 10^6$ cells/mL
 - Platelet count $\geq 1.0 \times 10^5$ cells/ μ L
 - Hemoglobin (Hgb) ≥ 10.0 g/dL
 - Creatinine ≤ 1.5 mg/dL
 - Total bilirubin ≤ 1.5 x upper limit of normal (ULN)
 - Alanine aminotransferase (ALT) ≤ 2.0 x ULN
 - Aspartate aminotransferase (AST) ≤ 2.0 x ULN

6.2 Exclusion Criteria

A subject will not be eligible for participation in this study if *any* of the following criteria apply.

- 6.2.1. Former therapy for prostate cancer (local or systemic)
- 6.2.2. Any previous prostatic surgical procedure that significantly changes the anatomy of prostate (at the discretion of sponsor's Medical Monitor)
- 6.2.3. Any investigational product received for prostate cancer
- 6.2.4. Prostate biopsy specimen reveals neuroendocrine or small cell features
- 6.2.5. Primary Gleason score is ≥ 4 or any Gleason pattern 5
- 6.2.6. Any evidence of locally advanced, regional or metastatic disease, including regional and distant lymph node enlargement (Nodes ≥ 1.5 cm in the short axis are considered pathologic and measurable) ([Scher, 2016](#))
- 6.2.7. A history of a cerebrovascular event (CVE) or transient ischemic attack (TIA)
- 6.2.8. Subject has used a 5-alpha-reductase inhibitor (e.g., finasteride or dutasteride) continuously for ≥ 6 months and within 6 months prior to study Screening
- 6.2.9. Subject has a history of any other stage I-IV malignancy, except for basal or squamous cell skin cancer. The subject must be disease free and off any malignancy-related treatment for at least 5 years.
- 6.2.10. Subject has prior use within 30 days of study Screening of any herbal, dietary, or alternative anti-cancer treatment or product, such as PC-SPES (or PC-x product), saw palmetto, ketoconazole, an estrogen-containing nutraceutical, or high dose calcitriol (>0.5 $\mu\text{g}/\text{day}$). The Investigator will consider herbal therapies on a case-by-case basis to determine whether they fall into the category of prohibited medications based on their potential for hormonal or anti-cancer or anti-cancer properties.
- 6.2.11. Need for systemic chronic immunosuppressive therapy (e.g., anti-tumor necrosis factor alpha monoclonal antibodies, glucocorticoids)
- 6.2.12. Uncontrolled, concurrent illness including, but not limited to the following: ongoing or active infection (bacterial, viral, or fungal), symptomatic congestive heart failure (New York Classification III-IV) ([Appendix 6](#)) or unstable angina pectoris within the last 6 months, or psychiatric illness that would limit compliance with study requirements as well as any condition that would preclude a subject from undergoing leukapheresis (e.g., within the previous 6 months: myocardial infarction, interventional cardiology procedure such as angioplasty or stent placement, pulmonary embolism or deep vein thrombosis).

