6.2.13. Hypogonadal (T < 175 ng/dL) or on continuous testosterone replacement therapy

6.2.14. Positive serology for HIV-1, HIV-2 or HTLV-1, HTLV-2

6.2.15. Active hepatitis B or C (See [Appendix 8](#) and [Appendix 9](#) for definitions)

6.2.16. Any medical intervention, any other condition, or any other circumstance which, in the opinion of the investigator or the sponsor's Medical Monitor, could compromise adherence with study requirements or otherwise compromise the study's objectives.

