6.6 Permitted Therapies

Subjects should receive full supportive care in accordance with standard practice at the clinical trial site.

Subjects who are receiving non-prostate cancer therapies (prescription or over-the-counter) at the time of randomization (that are not restricted ([Section 6.7](#))) should continue per the discretion of the prescribing physician.

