6.7 Restricted Therapies During Sipuleucel-T Treatment Period

Certain therapies and procedures could confound the results of this study. Therefore, subjects who are randomized to the sipuleucel-T arm and receive any of the following, 30 days prior to the first infusion until 30 days after the last infusion, will discontinue sipuleucel-T treatment (Section 6.3.1):

- Any immunosuppressive therapy, including systemic steroids. Use of inhaled, intra-nasal, intra-articular, and topical steroids is allowed. Oral or IV steroids to prevent or treat IV contrast reactions are allowed
- Blood products
- GM-CSF or G-CSF
- Any vaccinations

Subjects that discontinue sipuleucel-T treatment and have received > 0 mL of sipuleucel-T will remain in the Active Phase and follow the schedule of events (Table 1).

6.8 Restricted Therapies from Randomization to End of Active Phase (Sipuleucel-T and Control Arms)

Certain therapies and procedures could confound the results of this study. Therefore, subjects who receive any of the following will go from Active Phase of the study to the Follow-up Phase of the study:

- Any local or systemic therapy or procedures for prostate cancer (e.g., ADT, radical prostatectomy, external beam radiation or brachytherapy)
- Any local or systemic therapy or procedure targeting the prostate (e.g., transurethral resection of the prostate (TURP) or 5-alpha reductase inhibitor)
- Major surgery at the discretion of the sponsor's Medical Monitor
- Any investigational product for prostate cancer or other condition (per sponsor's Medical Monitor approval)
- Any other therapy at the discretion of the sponsor's Medical Monitor

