10.5 Analysis of Study Endpoints

10.5.1 Primary Endpoint

The primary endpoint is the proportion of subjects without a histopathologic upgrade over the 36-months following randomization and will be summarized by study arm. The primary endpoint for each subject is dichotomous with success defined as having been observed to be free of histopathologic upgrade at Biopsy 2 33 to 39 months after randomization. Histopathologic upgrading occurs when a subject with ISUP Grade Group 1 prostate cancer, at randomization, is upgraded to Grade Group 2 or higher, or a subject with ISUP Grade Group 2 prostate cancer, at randomization, is upgraded to Grade 3 or higher as determined by BICR, at any post-randomization biopsy. Histopathologic status is determined by biopsy and will be assessed at the scheduled biopsy or at any biopsy that is taken during radical-prostatectomy or

other time-point. Subjects upgrading before 36 months, or those found as upstaged at Biopsy 2, or those not observed at 36 months (i.e., do not complete Biopsy 2 prior to 39 months post randomization) will be regarded as failures in the primary analysis.

The primary analysis null hypothesis, $H_0: \Omega \leq 1$, versus the alternative hypothesis, $H_A: \Omega > 1$; where Ω is the odds of success in the sipuleucel-T arm over the odds of success in the control arm. The Cochran-Mantel-Haenszel (CMH) test, stratified by ISUP Grade Group 1 or 2 and the number of biopsies showing the presence of disease prior to registration will be used to estimate the odds ratio, and will be computed using exact methods based on Monte Carlo computations due to the potential for small frequencies.

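### Protocol 6.2.8, 6.6 and 6.8 conflict: a man on a 5-alpha-reductase inhibitor for under 6 months can be eligible, may continue it, and is then moved out of the phase that holds the endpoint biopsies

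*Protocol*

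**What the plan says.** **Entry.** Protocol 6.2.8 (repeated as exclusion 8 in the synopsis) bars a man if: "Subject has used a 5-alpha-reductase inhibitor (e.g., finasteride or dutasteride) continuously for ≥ 6 months and within 6 months prior to study Screening". Both conditions must be met.

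**Continuation.** Protocol 6.6 covers "Subjects who are receiving non-prostate cancer therapies (prescription or over-the-counter) at the time of randomization". Those not restricted under 6.7 "should continue per the discretion of the prescribing physician". The 6.7 list contains immunosuppressives, blood products, growth factors and vaccinations, and no 5-alpha-reductase inhibitor. Section 6.6 does not mention 6.8.

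**Removal.** Protocol 6.8 applies to both arms from randomization to the end of the Active Phase. It names "Any local or systemic therapy or procedure targeting the prostate (e.g., transurethral resection of the prostate (TURP) or 5-alpha reductase inhibitor", and a man who receives such a therapy "will go from Active Phase of the study to the Follow-up Phase of the study". Use already under way at randomization is not exempted. SAP 6.1 confirms that the Active Phase stops when a 6.8 therapy is received.

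**Endpoint.** Biopsies 1 and 2 are Active Phase procedures (Protocol 5.1 and the schedules of events). Protocol 10.5.1 says that men who "do not complete Biopsy 2 prior to 39 months post randomization) will be regarded as failures in the primary analysis". SAP 8.1.1 likewise counts a missing Biopsy 2 grade as failure, but it accepts a centrally read unscheduled or end-of-study biopsy within 90 days of the 36-month visit as a substitute.

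**The concern.** Read together, the three sections admit a man, allow his drug to continue, and then take him out of the only phase with scheduled biopsies because of that drug. His primary outcome then depends on an administrative move and not on his histology.

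Two things are at stake. First, men who fail for lack of a biopsy, whatever their arm, dilute the difference the trial is sized to detect. Second, sites that notice the conflict have no single instruction. In an open-label trial, some may move the man, some may overlook 6.8, and some may use the discretionary exclusion in 6.2.16. Protocol 6.8 itself says that the therapies it lists could confound the results, so handling should not be left to vary.

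**Working it through.** **1. Follow one man through the text.** He has taken the drug for 4 months and is still taking it at randomization.

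| Step | Section | Result |
|---|---|---|
| Excluded? | 6.2.8 | No: under 6 months of continuous use |
| Must the drug stop? | 6.6 and 6.7 | No: 6.7 does not list the class; it may continue at the prescriber's discretion |
| Phase after randomization | 6.8, SAP 6.1 | Follow-up Phase |
| Biopsies scheduled there | 5.1, Tables 1 and 2 | None |
| Central reading of unscheduled biopsies | 8.11 | Arranged during the Active Phase only |
| Primary analysis | 10.5.1, SAP 8.1.1 | Failure, unless a centrally read biopsy falls within 90 days of the 36-month visit |
| Last-observation-carried-forward analysis | SAP 12.6.1.3 | Success if no upgrade is seen |
| Per-protocol set | SAP 9.2 | Outside it without a month-36 grade |

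**2. Reproduce the stated power.** Inputs from Protocol 10.1: 300 versus 150 men, success 0.84 versus 0.70, one-sided alpha 0.025.

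- Odds ratio: (0.84/0.16)/(0.70/0.30) = 5.25/2.333 = 2.25, as stated.
- Unstratified Fisher exact power, summing the joint binomial probabilities of all tables with one-sided p ≤ 0.025: 90.3%. The continuity-corrected pooled z gives 90.2%. Both agree with the stated 90%.
- The uncorrected pooled z gives 92.1%, so it is not used below. The planned test is an exact stratified one, and Fisher is the closer stand-in.

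**3. Size of the dilution.** The documents give no share of men on the drug at randomization. Assume that a share *f* of each arm is affected, that all of them fail, and that they would otherwise have succeeded at their arm's planned rate. Success becomes 0.70(1 − *f*) versus 0.84(1 − *f*). At *f* = 0.02, for example, 0.70 × 0.98 = 0.686 and 0.84 × 0.98 = 0.823.

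| *f* | Men of 450 | Control | Sipuleucel-T | Odds ratio | Fisher exact power |
|---|---|---|---|---|---|
| 0 | 0 | 0.700 | 0.840 | 2.25 | 90.3% |
| 1% | 4.5 | 0.693 | 0.832 | 2.19 | 88.9% |
| 2% | 9 | 0.686 | 0.823 | 2.13 | 87.6% |
| 5% | 22.5 | 0.665 | 0.798 | 1.99 | 83.1% |

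**4. Unequal handling, as a hypothetical only.** Suppose there is no treatment effect (0.70 in both arms), 2% of controls are moved and fail, and no sipuleucel-T man is moved. Control success is 0.70 × 0.98 = 0.686, a gap of 1.4 points. The one-sided Fisher exact rejection rate rises from 2.0% to 3.9%.

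**The case against.** The strongest reply is that this is a missing cross-reference and little more. Protocol 8.9 sends sites to both 6.7 and 6.8 for restricted therapies, so a careful site would find 6.8. Section 6.6 leaves continuation to the prescriber and orders nothing. Section 6.2.16 lets the investigator or Medical Monitor exclude a man whose circumstances "could compromise adherence with study requirements or otherwise compromise the study's objectives". All of this stands, and it limits how often the conflict will matter. It does not remove it: finding 6.8 only confirms that an eligible man must leave the Active Phase, and a discretionary exclusion is one more way for sites to differ.

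A reader might infer three stronger things that the documents do not support.

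- *That such a man is a primary failure from the day he is randomized.* Nothing makes use of the drug, or leaving the Active Phase, a failure in itself. Failure comes from a missing Biopsy 2 grade, and SAP 8.1.1 leaves a way to fill it. That route is weak, because no Follow-up Phase biopsy is scheduled and 8.11 arranges central reading only in the Active Phase, but it exists.
- *That he loses his sipuleucel-T infusions.* Section 6.7 says its therapies end treatment. Section 6.8 does not, and 6.3.1 does not name 6.8 therapies as a reason to discontinue. The text leaves this open.
- *That type I error is inflated.* Section 6.8 binds both arms alike, and nothing suggests that only controls would be moved. The 3.9% figure belongs to that hypothetical alone.

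**Conclusion.** The contradiction between 6.2.8, 6.6 and 6.8 is in the text and needs no assumption. An affected man is an expected, not an automatic, primary failure. The same man, with no upgrade seen, is a success under last observation carried forward and is outside the per-protocol set, so the sensitivity analyses do not settle how he should count.

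The numerical effect rests entirely on assumed prevalence. The group is narrow, being men who started within the last 6 months and are still on the drug at randomization, and it is probably small. At 1% to 5% of both arms, all failing, the loss is 1.4 to 7.2 percentage points of power (90.3 − 88.9 and 90.3 − 83.1). No stated figure in the plan is wrong on this account. The point is worth correcting because the correction is cheap and the rule touches the primary endpoint; it does not threaten the design.

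**What to change.** Reconcile Protocol 6.2.8 (with synopsis exclusion 8), 6.6 and 6.8 so that no man is eligible at entry while already meeting a 6.8 removal condition. Make 6.6 refer to 6.8 as well as 6.7. Apply the reconciled rule equally in both arms. Which clinical rule to adopt is for the sponsor to decide, and the entry criterion and the on-study restriction need not be identical as long as they no longer collide.

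The SAP should also say explicitly how men moved to the Follow-up Phase under 6.8 are classified in the primary analysis.

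The cost is amendment wording in a few sections, one clarifying sentence in the SAP and, depending on how the sponsor reconciles the passages, a slightly smaller eligible pool.

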6.2.13. Hypogonadal (T < 175 ng/dL) or on continuous testosterone replacement therapy

6.2.14. Positive serology for HIV-1, HIV-2 or HTLV-1, HTLV-2

6.2.15. Active hepatitis B or C (See [Appendix 8](#) and [Appendix 9](#) for definitions)

6.2.16. Any medical intervention, any other condition, or any other circumstance which, in the opinion of the investigator or the sponsor's Medical Monitor, could compromise adherence with study requirements or otherwise compromise the study's objectives.

6.3 Discontinuation from Study

A subject may discontinue participation in the trial at any time without prejudice. If a subject withdraws consent for any further study involvement, complete withdrawal of consent must be documented in the subject's medical record. The date and reason for withdrawal will be recorded in the subject's medical record and on the eCRF.

Whenever possible, every subject who withdraws consent and discontinues from the study will undergo an Early Withdrawal Visit within 30 days following discontinuation notice. Subjects are encouraged to have, as standard of care, a systematic prostate biopsy (≥ 10 cores) with or without MRI at the investigator's discretion prior to study withdrawal. The H&E and special-stained slides from this biopsy will be submitted for BICR determination of their ISUP Grade Group classification prior to study withdrawal. All AEs considered by the investigator to be related to sipuleucel-T that are ongoing at the time of discontinuation will be followed by the investigator until resolution, return to baseline, or a determination by the investigator that no further improvement is expected. The investigator should make every reasonable attempt to ensure that the subject is contacted (via telephone or during the Early Withdrawal Visit) to obtain the final status of any AEs and concomitant medications.

6.3.1 Discontinuation from Sipuleucel-T Arm

Declining the first sipuleucel-T infusion or associated leukapheresis will result in an automatic withdrawal from the study. Subjects will complete an early withdraw visit within 30 days of the scheduled sipuleucel-T infusion.

Sipuleucel-T will be discontinued if a subject meets any of the following criteria:

- The subject never undergoes a leukapheresis for the purpose of receiving sipuleucel-T
- The subject undergoes leukapheresis, but is unable to receive at least 1 partial (>0 mL) sipuleucel-T infusion for any reason at the discretion of sponsor's Medical Monitor
- Inability to manufacture sipuleucel-T in the opinion of the sponsor's medical monitor
- The subject experiences intolerable toxicity
- Significant infection at the discretion of sponsor's Medical Monitor

- CVE or TIA of any grade prior to completion of 3 sipuleucel-T infusions
- Withdrawal of consent for continued sipuleucel-T infusions
- The subject fails to comply with protocol-specified procedures or protocol requirements
- Sponsor terminates the study
- The subject is discontinued from the study at the discretion of the investigator or sponsor

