6.3.2 Discontinuation from Study Participation

A subject in either the sipuleucel-T or control study arms will end study participation, including discontinuation of sipuleucel-T (sipuleucel-T arm only), biopsy and blood sample collection, for any of the following reasons:

- The subject withdraws consent or loses the ability to provide informed consent to participate in the study for any reason
- The subject is diagnosed with locally advanced or metastatic prostate cancer
- The subject dies or is lost to follow-up ([Section 6.5](#))

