6.4 Replacement of Subjects

Subjects who are randomized to the sipuleucel-T arm, but do not receive any sipuleucel-T (>0 mL) may be replaced.

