9.0 Analysis Sets

9.1 Intention-to-Treat (ITT)

The ITT analysis set is defined as all randomized subjects, regardless of whether any dose of treatment was received. Subjects in this analysis set will be analyzed according to the study treatment assigned at randomization. Subjects who are randomized into the sipuleucel-T arm but are replaced per protocol section 6.4 (as described below), will be included in the ITT analysis set. This analysis set will be used for the primary analyses of the primary endpoint and the secondary efficacy endpoints.

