12.6.1.3 Sensitivity Analyses

To evaluate the impact of the potential asymmetric drop-outs, the exact Cochran-Mantel-Haenszel test of the null hypothesis of no difference in the odds of no ISUP grade group upgrade across treatment arms, while accounting for stratification by baseline ISUP grade group and number of biopsies, will be repeated in the per protocol analysis set as a sensitivity analysis.

In a separate sensitivity analysis, the last observation carried forward method will be applied to the primary endpoint in the ITT analysis set. In other words, all subjects with non-missing ISUP grade group at baseline and without any upgrading within 36 months after randomization (even without any post-randomization ISUP grade group) will be counted as successes in the primary efficacy endpoint. Subjects upgrading before 36 months, those with an upgrade at Biopsy 2, or those with missing ISUP grade group at baseline will be counted as failures.

Three sipuleucel-T subjects were replaced pursuant to protocol section 6.4. Sensitivity analyses will be conducted to evaluate the impact, if any, of the inclusion of these subjects in the analysis of the primary and secondary endpoints.

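### Declining the first leukapheresis or infusion removes a sipuleucel-T man from the whole study, with no matching control rule, so obtainable outcomes are lost in one arm; a moderate problem with a cheap fix

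*Protocol*

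**What the plan says.** Protocol 6.3.1, which applies to the sipuleucel-T arm only, reads: "Declining the first sipuleucel-T infusion or associated leukapheresis will result in an automatic withdrawal from the study". An early withdrawal visit follows within 30 days of the scheduled infusion.

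Protocol 6.3.2 lists the exit reasons common to both arms, beginning "A subject in either the sipuleucel-T or control study arms will end study participation". They are withdrawn or lost consent, locally advanced or metastatic disease, death, and loss to follow-up. Declining treatment is not among them.

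Protocol 6.7, on restricted therapies, treats men who stop after some product differently: "Subjects that discontinue sipuleucel-T treatment and have received > 0 mL of sipuleucel-T will remain in the Active Phase".

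Protocol 6.4 adds: "Subjects who are randomized to the sipuleucel-T arm, but do not receive any sipuleucel-T (>0 mL) may be replaced".

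For analysis, SAP 9.1 says: "The ITT analysis set is defined as all randomized subjects, regardless of whether any dose of treatment was received". It adds that men who "are replaced per protocol section 6.4 (as described below), will be included in the ITT analysis set". Protocol 10.5.1 says that men who "do not complete Biopsy 2 prior to 39 months post randomization) will be regarded as failures in the primary analysis", and SAP 8.1.1 likewise scores a missing Biopsy 2 grade as failure. The last-observation-carried-forward (LOCF) analysis in SAP 12.6.1.3 scores a man with a baseline grade and no observed upgrade as a success, even with no post-randomization grade.

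**The concern.** The protocol already separates stopping treatment from leaving the study, but not for men who decline at the outset. Such a man may be willing to stay on active surveillance under observation. At entry he agreed to two on-study standard-of-care biopsies (inclusion criteria in the Synopsis and Protocol 6.1). The rule removes him anyway, whereas a control man who is unhappy with his assignment stays unless he withdraws consent.

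The first leukapheresis is due within 60 days of randomization, so a biopsy at early withdrawal, which is only encouraged, comes far too early to give a grade at 33 to 39 months.

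At stake are the size of the primary odds ratio and the power to detect it. Quality-of-life and subsequent-treatment data are also cut short for the same men. No planned analysis recovers the outcomes:

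- The primary analysis scores these men as failures.
- LOCF scores them as successes unless an upgrade was seen.
- The per-protocol set excludes them, since it requires all three infusions and a month-36 grade.
- The replaced-subject analysis examines only the effect of including three such men.

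**Working it through.** **Inputs from the documents** (Protocol 10.1, SAP 6.2): success 0.84 against 0.70, 300 against 150 men, one-sided alpha 0.025, stated power 90%. **Assumed inputs:** the share x of the sipuleucel-T arm that declines (1% to 5%), and success of 0.70, the control rate, for a decliner who reaches Biopsy 2.

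**Formula.** Power = Φ{[(pS − pC) − 1.96·SE0]/SE1}, where SE0 uses the pooled proportion and SE1 the separate proportions.

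**The plan's own figure.** The pooled proportion is (300 × 0.84 + 150 × 0.70)/450 = 0.7933, so SE0 = 0.0405 and SE1 = 0.0430. Power = Φ[(0.14 − 1.96 × 0.0405)/0.0430] = 92.1%. Fisher exact power is 90.3%, and the continuity-corrected total sample size is 447 against the planned 450. The odds ratio is (0.84/0.16)/(0.70/0.30) = 2.25. The stated 90% reproduces.

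**Effect of the rule, no control loss.** Expected sipuleucel-T success is:

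- decliners scored as failures: 0.84(1 − x)
- all followed to Biopsy 2: 0.84(1 − x) + 0.70x
- half reach Biopsy 2, the rest failures: 0.84(1 − x) + 0.35x

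| x (men of 300) | Failures: success, OR, power | All followed: success, OR, power | Half followed: success, power |
|---|---|---|---|
| 1% (3) | 0.8316, 2.12, 88.3% | 0.8386, 2.23, 91.5% | 0.8351, 90.0% |
| 3% (9) | 0.8148, 1.89, 77.6% | 0.8358, 2.18, 90.3% | 0.8253, 84.8% |
| 5% (15) | 0.7980, 1.69, 63.3% | 0.8330, 2.14, 89.0% | 0.8155, 78.2% |

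Fisher exact power is lower but shows the same pattern: 85.8% as failures against 89.6% all followed at 1%, and 58.2% against 86.6% at 5%.

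**The one documented count.** SAP 12.6.1.3 says: "Three sipuleucel-T subjects were replaced pursuant to protocol section 6.4". Suppose all three were decliners and their replacements bring the arm to 303, with 300 × 0.84 = 252 expected successes among the other men:

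- as failures: 252/303 = 0.8317, power 88.5%
- all three followed: (252 + 3 × 0.70)/303 = 0.8386, power 91.6%
- as LOCF successes: 255/303 = 0.8416, power 92.8%

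The cost against full follow-up is about 3 points.

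**Type I error.** With no true effect (0.70 in both arms), scoring decliners as failures gives a sipuleucel-T rate of 0.70(1 − x), which is below control. One-sided rejection falls from 2.5% to 1.7% at x = 1% and 0.3% at 5%. LOCF gives 0.70(1 − x) + x, and rejection rises to 2.9% and 5.3% (normal approximation).

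**Control dropout.** Controls who miss Biopsy 2 are also failures. With an assumed 1% loss in the sipuleucel-T arm and 2% in control, the rates are 0.84 × 0.99 = 0.8316 and 0.70 × 0.98 = 0.686. The odds ratio is (0.8316/0.1684)/(0.686/0.314) = 2.26, about the design value.

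**The case against.** The strongest reply concerns size. The only figure in the documents is three replaced men, about 1% of 300. SAP 9.1.1 describes candidates for replacement as men found ineligible after randomization or who withdrew consent before treatment. An ineligible man did not decline, and a man who withdrew consent leaves under 6.3.2 whatever 6.3.1 says. The documented number forced out by this rule could be zero. This stands. Unreplaced decliners are possible, but no count is given.

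A reader might infer that the trial faces power of 63% to 78%. The documents do not support that: those values need decline rates of 3% to 5%, which are assumptions. A reader might also infer that follow-up would restore 89% to 92% power. That requires every decliner to complete Biopsy 2, and men who refused the first study procedure may not.

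A third tempting inference is that the final odds ratio must be biased against sipuleucel-T. Only the rule's own contribution has that sign. In an open-label trial controls may also leave, and the example with 2% control loss cancels the effect.

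The loss in power comes through scoring a missing Biopsy 2 as failure, so it overlaps any criticism of that scoring and should not be counted twice. The sentence in 6.7 concerns restricted therapies and does not itself say that men with 0 mL leave the study. The power formula is not the planned exact stratified test.

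The primary and LOCF analyses do score unobserved decliners in opposite ways, and for three men the gap is narrow. They do not supply the missing outcomes, and LOCF favours sipuleucel-T when loss is confined to that arm.

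**Conclusion.** The point holds, at moderate severity. Protocol 6.3.1 ends observation of men whose outcomes could still be collected, in one arm only, and no planned analysis replaces those outcomes. The men themselves stay in the ITT set; what is lost is their data. The rule cannot by itself produce a false-positive primary result. Its cost is a lower odds ratio and lower power.

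The cost is about 3 points of power if the three replaced men were all decliners, less if they were not, and more if there were further decliners who were not replaced. These sizes rest on the design success rates, an assumed 0.70 success for followed decliners, and no control loss. The material does not support calling this a defect that must be corrected before the trial can be interpreted.

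**What to change.** Reconcile Protocol 6.3.1, 6.3.2 and 6.7 on the study follow-up of men who received no product, so that declining sipuleucel-T does not by itself end study participation. Unless he withdraws consent for follow-up, such a man would continue outcome collection on the Table 2 schedule: Biopsy 1, Biopsy 2, patient-reported outcomes and subsequent prostate cancer treatment. The change concerns data collection only. Report the number of decliners, replaced or not, separately from men found ineligible and men who withdrew consent.

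The cost is a short amendment and follow-up of a few extra men, on biopsies they accepted at entry. Some will still leave and remain failures in the primary analysis. The SAP already reports replacements in the past tense, so men already withdrawn could be recovered only with new consent.
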